As a chronic noncommunicable disease, maintaining long-term adequate blood glucose control can greatly improve the prognosis and reduce the burden on individuals and society. At present, in diabetes treatment, insulin is still the "ultimate weapon" to control blood sugar, based on real-world research which shows that about 1/4 of diabetic patients are currently receiving insulin therapy [2]. However, despite continuous improvements in devices and drugs over the past 100 years since the invention of insulin, the average glycated hemoglobin (Hemoglobin A1c, HbA1c) of insulin users is still as high as 8.5%, with only about 1/3 reaching the guideline recommended range of less than 7.0%, and 1/3 exceeding 9.0% [3,4].

A growing number of studies have shown that continuous adjustment of insulin injection doses according to inter- and intra-individual differences can improve the effectiveness of insulin therapy in blood glucose control [5]. However, in clinical practice, due to the limitations of consultation time, resources, and patients' ability to receive relevant training, the average dose adjustment cycle of patients receiving insulin therapy is 3-6 months. At the same time, a study in type 2 diabetic patients receiving insulin therapy showed that insulin therapists often failed to use insulin doses that satisfactorily controlled their blood glucose [6]. How to adjust the dose of adjuvant insulin therapy more effectively and safely and promote the translation of guideline opinions into clinical practice is an urgent problem in the field of diabetes treatment.

In type 1 diabetes, the "artificial pancreas," or closed-loop insulin pump, can hopefully bridge the gap between guidelines and reality. It monitors blood glucose in real time and enables precise dose adjustment of insulin injections, and related studies have also shown its advantages in blood glucose control [7]. A randomized controlled study by Thabit et al. in children and adults with type 1 diabetes showed that closed-loop insulin pumps were able to reduce HbA1c from 8.5% to

7.5% without increasing the occurrence of hypoglycemia [8]. However, the high cost of closed-loop insulin pumps limits their use in the larger population of type 2 diabetes.

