Some self-glucose monitoring devices can upload blood glucose values to medical staff in the form of remote data transmission to help patients adjust insulin doses under the guidance of medical professionals [9]. Some devices then accept blood glucose data and give recommendations for adjusting the dose of insulin according to a preset algorithm, which is provided to medical staff, who then pass on to patients through voice or video communication [10]. However, these tools still depend on the involvement of healthcare providers, who have very limited time to allocate to these aspects in practice. At the same time, there are mobile phone apps that digitize insulin dose adjustment methods to help patients adjust insulin doses; The apps are approved by the US Food and Drug Administration (USFDA), require a clinician's prescription to obtain them [11]; although these apps have long existed, diabetics treated with insulin have not seen improvement in recent years [3].

In recent years, the rapid development of bioinformatics and big data science has brought new opportunities and means for disease prevention, diagnosis and treatment. The d-Nav insulin Guidance System (Insulin Guidance System) developed by Hygieia in the United States was officially launched in the UK in 2012, which can provide guidance and suggestions for the dose of insulin injection by analyzing the results of self-blood glucose monitoring data and previous insulin injection doses, combined with blood glucose values before insulin injection. The randomized controlled clinical study [2] published by Lancet in February 2019 in people with type 2 diabetes showed that HbA1c levels decreased by 1% from baseline 8.7% in the intervention group after 6 months of using the d-Nav insulin injection dose guidance system supplemented by physician guidance, and the control group reduced HbA1c by 0.3% from 8.5% after only 6 months under physician guidance ($p < 0.0001$). This suggested that the d-Nav insulin injection dose guidance system supplemented with physician-guided glycemic control was significantly better than physician-guided alone.

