This is a single-blind, parallel (two-arm), randomized controlled, prospective, non-inferiority trial aiming to assess the efficacy and safety of a proposed artificial-pancreas-like algorithm (AP-A) in MDI therapy in type 2 diabetes.

Hypothesis: Adopting AP-A in guiding pre-prandial insulin titration is non-inferior to the standard clinical approach provided by diabetes specialists from academic center.

Study Population

Sample Size:

We hypothesized that use of the AP-A would not be inferior to physician-guided recommendations in percentage of sensor readings within the target range of 3.9–10 mmol/L. For the sample size calculation, data from the JDRF CGM randomized controlled study and the REPLACE-BG study were used to estimate the properties of the primary endpoint and to define the non-inferiority limit. The sample size was calculated using PASS 15.0 for non-inferiority

analysis, with a margin of 7.5% between arms in a parallel study design with a power of 90%, a one-sided significance level of 5% and SD of 13%. The resulting analysis showed that 106 subjects were needed for the study. The sample size was set at 111-116 participants (we rounded it off to about 120), given an estimated 5–10% dropout rate, with randomization in a 1:1 ratio between the two study arms.

Inclusion Criteria:

Type 2 diabetes subjects receiving intensive insulin therapy;

Age \geq 18;

Unsatisfied glucose control, HbA1c \geq 8.0%.

Exclusion Criteria:

Type 1 diabetes;

Currently pregnant, planning to be pregnant or unwilling and unable to use contraception during the study (female only);

Mental disorders;

Refusion to wear invasive examination equipment;

Reasons for not able to wear intermittently scanned continuous glucose monitoring (isCGM), e.g., serious allergies, skin diseases, etc.;

Participants who have skin lesions, scarring, redness, infection or edema at the sensor application site that may affect the accuracy of the sensor;

Serious comorbidities, including but not limited to heart disease, cerebrovascular disease, liver and kidney disease, and serious diabetes complications;

Anticipated X-ray, MRI or CT examination during the study;

Usage of drugs that affect blood glucose, such as glucocorticoids, one-month prior enrollment;

Any other reason that investigators assessed to be unsuitable to participate in the study.

Design

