4.1 Population

4.1.1 Sample size

The main study is a randomized controlled trial with noninferiority design. Participants will be assigned 1:1 to either the AP-A arm or the physician arm. We hypothesized that use of the AP-A would not be inferior to physician-guided recommendations in percentage of sensor readings within the target range of 3.9–10 mmol/L. For the sample size calculation, data from the JDRF CGM randomized controlled study and the REPLACE-BG study were used to estimate the properties of the primary endpoint and to define the non-inferiority limit [1][2]. The sample size was calculated using PASS15.0 for non-inferiority analysis, with a margin of 7.5% between arms in a parallel study design with power of 90%, a one-sided significance level of 5% and SD of 13%. Besides, we assume that there is no difference between the two arms in achieving the percentage time of sensor readings within the target range of 3.9–10 mmol/L. The equation for calculating the sample size is as follow [3][4]:

$$n = 2 \frac{(z_{1-\alpha} + z_{1-\beta})^2 S^2}{(\Delta - \delta)^2}$$

In the equation, n is the sample size of each arm, Δ is the non-inferiority margin of the

primary endpoint, δ is the mean difference at which the power is computed, α is the type I error, β is the type II error, and S^2 is the pooled standard deviation of both comparison arms. The resulting analysis showed that 106 subjects were needed for the study. Finally, the study enrolled 119 participants, which met the sample size requirement.

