5.1 Data management and general analysis

Electronic dataset system will be used for data collection and management. The data analyses mainly include statistical description and statistical inference. Quantitative data will be described by central tendency and dispersion tendency. The normally distributed data of central tendency and dispersion tendency will be described as means and standard deviation, respectively. The non-normally distributed data of central tendency and dispersion tendency will be described as median and quartiles. The qualitative data will be described as frequency and percentage. Statistical inference, independent *t* test or non-parameter test will be used to compare the quantitative data between the two arms, while chi-square test or Fisher's exact test will be used for comparing the qualitative data between the two arms.

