5.2 Analysis of primary endpoints

For the co-primary endpoint comparisons, the statistical analysis will be performed to evaluate the differences between the two groups for the two primary endpoints during MDI therapy. Specifically, the co-primary endpoints used a stepdown strategy designed to maintain type I error at 5% or less for multiple comparisons. The primary endpoint followed no Gaussian distribution, will be presented as median (interquartile range). The mean (95% confidence intervals, CIs) of between-group differences of the median will be calculated by bootstrap method (1000 replications). For the primary efficacy endpoint, non-inferiority will be established if the lower bound of the CI does not less than the noninferiority margin of -7.5%. For the primary safety endpoint, non-inferiority will be established if the upper bound of the CI does not greater than the non-inferiority margin of 2%, which is selected according to previous reports [1][5]. The per-protocol (PP) sets will be also used for sensitivity analysis.

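### Optional improvement: no prespecified rule lets a lower confidence limit above 0 on time in range count as a confirmatory superiority claim

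*Supplement*

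**What the plan says.** The protocol (Purpose and Objectives) and the final SAP (section 1) carry the same single hypothesis: "Hypothesis: Adopting AP-A in guiding pre-prandial insulin titration is non-inferior to the standard clinical approach provided by diabetes specialists from academic center". The aim in SAP section 1 is to find out whether algorithm-guided dosing under physician supervision matches physicians alone in effect and safety.

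SAP 4.1.1 sizes the trial for a 7.5-point margin and 90% power, at "a one-sided significance level of 5% and SD of 13" percent, and adds that "we assume that there is no difference between the two arms in achieving the percentage time of sensor readings within the target range". It reports 106 patients needed and 119 enrolled.

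SAP 5.2 gives the decision rule for TIR: "non-inferiority will be established if the lower bound of the CI does not less than the noninferiority margin of -7.5" percent. For time below 3.0 mmol/L the upper limit must not exceed 2%. The interval is a 95% bootstrap interval for the difference of medians.

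SAP 5.3 tests the secondary endpoints in a fixed order until one fails, with a 2% limit for the hypoglycaemia endpoints expressed as time in range. No section says what follows if the lower limit for TIR lies above 0. SAP 5.1 adds that a t test or "non-parameter test will be used to compare the quantitative data between the two arms", and SAP 5.5 sets two-sided 0.05. Neither is tied to TIR or given a place in the testing order.

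**The concern.** The protocol's background makes a benefit foreseeable. It says of routine care that "insulin therapists often failed to use insulin doses that satisfactorily controlled their blood glucose". Of an earlier randomised trial of another dose-guidance system added to physician care, it says: "This suggested that the d-Nav insulin injection dose guidance system supplemented with physician-guided glycemic control was significantly better than physician-guided alone". The present trial also compares guidance plus physician with physician alone.

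If TIR turned out clearly better with the algorithm, the plan's formal verdict would still be non-inferiority. An interval of (-6, +3) and one of (+2, +11) would receive the same label. A P value taken from the general tests in SAP 5.1 would have no prespecified standing as a superiority claim, and the plan's silence leaves that route open. At stake is how far a favourable result can be claimed. The validity of the non-inferiority conclusion is not affected.

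**Working it through.** **Inputs.** SAP 4.1.1: margin 7.5 points, SD 13, power 90%, one-sided 5%, true difference 0, 106 needed, 119 enrolled (taken as 60 and 59). SAP 5.2: two-sided 95% interval. The true gains used below are assumptions, because the documents give none.

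**1. The plan's own figure.** n per arm = 2 × (1.645 + 1.282)² × 13² / 7.5² = 51.5, so 52 per arm and 104 in total. With the t distribution it is 53 per arm, exactly the stated 106. At one-sided 2.5% it would be 128 (normal) or 130 (t), so 106 belongs to one-sided 5%.

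**2. Nesting.** A lower limit above 0 is also above -7.5. Superiority on TIR can therefore be declared only where non-inferiority has been. In 400,000 simulated trials at 53 per arm with the 95% interval, the chance of a false TIR claim was 2.5% at a true difference of -7.5 and 2.5% at 0.

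**3. Effect on the whole testing sequence.** Take a true TIR difference of 0 and a first secondary endpoint exactly at its null boundary. Non-inferiority on TIR then passes with probability 0.844 (53 per arm, 95% interval).
- *Superiority as an ungated branch beside the secondary endpoint, independent results:* 0.025 + 0.025 × (0.844 - 0.025) = 0.045. Simulation over correlations from -0.5 to 0.8 gave 3.6% to 4.5%.
- *Superiority in one fixed place, before or after the secondary endpoint:* about 2.5% or less in every simulated case.

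**4. Power of the superiority step** (normal approximation). For 60 and 59 patients, SE = 13 × √(1/60 + 1/59) = 2.38 and the half-width is 1.96 × 2.38 = 4.7 points. Power = 1 - Φ(1.96 - gain/SE). For a difference of medians with normal data, SE is multiplied by √(π/2) = 1.253, giving 2.99. SAP 5.2 says the primary endpoint is not Gaussian, so the medians column is only a guide.

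| True gain (points) | Means | Medians |
|---|---|---|
| 0 | 2.5% | 2.5% |
| 3 | 24% | 17% |
| 5 | 55% | 39% |
| 7.5 | 88% | 71% |
| 10 | 99% | 92% |

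The gain detectable with 80% power is (1.96 + 0.84) × SE. On means that is 6.7 points with 119 patients and 7.1 with 106 (SE 2.53). On medians with 119 patients it is 2.80 × 2.99 = 8.4.

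**5. Which interval.** These results hold for the 95% interval in SAP 5.2. A 90% interval, which would match "a one-sided significance level of 5% and SD of 13" percent, would put superiority at one-sided 5%, out of line with the two-sided 0.05 in SAP 5.5.

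**The case against.** The strongest reply is that nothing here is wrong. Aim, hypothesis, zero-difference assumption and decision rule all agree, and no passage states a superiority aim. The comparator is academic specialists titrating on sensor readings in hospital over an assumed 7 days, whereas the background's complaint concerns routine care with dose changes every 3 to 6 months. The encouraging earlier trial tested another system over 6 months on HbA1c. The sponsor's own preliminary work reports performance and doses similar to the comparators. All of this stands, and it is why the point carries low weight.

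A reader might infer that a clear benefit would be hidden. The documents do not support that. SAP 5.2 reports the difference with its 95% interval and SAP 5.4 adds a forest plot, so the two intervals contrasted above would look plainly different.

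A reader might also infer that the step is free wherever it is put. That is true for TIR alone. In the full sequence it needs one stated place, and a place in the middle has a price: under the planned zero difference it would fail 97.5% of the time and end confirmatory testing of everything after it.

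Timing is a fair objection too. The final SAP already reports 119 enrolled and the shape of the primary endpoint's distribution, and its change summary dates the secondary-endpoint amendments to after the study. SAP 2.3 says the statisticians are masked, but the documents do not say whether results by arm had been seen.

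What survives is narrow. A superiority claim on TIR has no prespecified route, and one can be provided within the existing error rate.

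**Conclusion.** This is an optional, low-weight improvement and not a defect. The non-inferiority design suits the aim, and the stronger readings (that the design is mistaken, or that a benefit would go unseen) do not hold. The plan lacks a rule that turns a lower limit above 0 on TIR into a confirmatory claim.

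With a single place in the fixed order, such a rule leaves the one-sided error at or below 2.5% and needs no more patients. Its yield is limited: about 2.5% under the planned zero difference, and 80% power only near a 7-point gain, almost the size of the margin itself. These figures assume SD 13, a comparison of means and a two-sided 95% interval. The SAP's difference of medians would lower the power, to about 71% at 7.5 points if the data were normal.

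**What to change.** Add to SAP 5.2 and 5.3, before any unblinded data are seen:

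*If non-inferiority is shown for both co-primary endpoints and for time below 3.9 and below 2.8 mmol/L (upper limit of the two-sided 95% CI not above 2%), superiority of AP-A on TIR is tested in the full analysis set from the same two-sided 95% CI (lower limit above 0).*

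Make this the last step of the fixed order, so that its failure blocks no other endpoint. Write the order out in full. Secondary endpoints without a stated margin cannot serve as steps and should be reported with their intervals. Any that are given a margin go ahead of the superiority step.

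Correct the sentence in SAP 5.3 on which the hypoglycaemia gate depends. As written, it declares non-inferiority when the upper limit exceeds the margin or the lower limit falls below it, the reverse of SAP 5.2.

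The cost is two short text changes, with no new data. Coming last, the superiority step is reached only if every earlier step passes. If results by arm have already been seen, a superiority reading of TIR can still be given but must be labelled exploratory.

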2.1 Ethical Approval

This study will be conducted in Peking University People's Hospital, Beijing, China. This study has been registered with Chictr.org (register number: ChiCTR2200055328), and approved by the institutional review board at Peking University People's Hospital (2020PHB338-01).

2.2 Study design

This is a single-blind, parallel (two-arm), randomized controlled, prospective, non-inferiority study. The participants will be randomly divided in 1:1 ratio into AP-A arm and the physician arm. This study aims to assess the efficacy and safety of a proposed AP-A in multiple daily injection (MDI) therapy in type 2 diabetes. In the AP-A arm, the recommended dose of insulin injection was given by the algorithm and implemented after the doctor's approval. The physician arm was given insulin injection dose directly by the physician.

2.3 Randomization and Blinding

After signing the informed consent forms, the participants will be enrolled according to the inclusion and exclusion criteria. The participants who meet the eligibility criteria will be randomized into two arms. Local investigators randomly allocated participants after their enrolment. The randomization was stratified by age and glycated hemoglobin A1c (HbA1c) at screening using a computer-generated random sequence, and had random block size. The participants and statisticians will be masked to the arm assignment, whereas physicians are not masked due to the nature of the intervention.

3 Study outcomes

3.1 Primary endpoints

The primary endpoint is the non-inferiority for percentage time spent with sensor glucose level in 3.9-10.0 mmol/L (70-180 mg/dL) between the two study arms. The primary safety endpoint is the percentage time spent with sensor glucose level below 3.0 mmol/L (54 mg/dL).

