Prepare the sensor applicator: completely tear the packaging film from the sensor assembly package, and unscrew the sensor applicator cover (note: the sensor code must match the sensor assembly package and the sensor applicator).

Align the black mark: Align the black mark on the sensor applicator with the black mark on the sensor assembly package. Press the sensor applicator firmly until it stops.

Lift the sensor applicator from the sensor assembly package.

The sensor applicator is ready to apply the sensor.

Application: Place the sensor applicator on the application part, and press down firmly to apply the sensor (Note: Do not press down before placing the sensor applicator on the prepared application part, to prevent unexpected results or injuries).

Gently remove the sensor applicator from the patient.

Ensure that the sensor is firmly applied. Discard the used sensor applicator and sensor assembly package.

- In the intervention AP-A arm, isCGM data are collected before meal and uploaded into the proposed closed-loop meal-bolus decision algorithm, which could automatically output suggested insulin dosage. The physician would review the suggested dosage and choose either to adopt it, or override the recommended dosage. In the physician arm, insulin dosage adjustment is determined by certified endocrinologists according to current clinical strategies based on isCGM readings.
- The titration period will depend on the actual hospitalization days. We assume that the hospitalization period is 7 days, and the titration period will be 7 days (Figure 5).

[figure not shown]

Figure 5. Study procedure

- After the participants are discharged from the hospital, both arms are treated according to physician's instructions.
- Outpatient appointment visit 14 days after enrollment. During the visit, isCGM data will be downloaded and instructions according to the isCGM data will be shared with participants. The participants will then be treated according to routine treatment. 2 ml of blood will be taken for examination of glycosylated albumin. And the study follow-up is over.

Statistical Methods, Data Analysis and Interpretation

Sample Size and Randomization:

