This single-blind, parallel (two-arm), randomized controlled, prospective, non-inferiority trial aims to determine whether pre-prandial insulin dose adjustments guided by the artificial-pancreas-like algorithm (AP-A) under the supervision of physicians is as effective and safe as those guided by physicians alone.

Hypothesis: Adopting AP-A in guiding pre-prandial insulin titration is non-inferior to the standard clinical approach provided by diabetes specialists from academic center.

2 Methods

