3.2 Secondary endpoints

- 1) Proportion of isCGM stored glucose data < 3.9mmol/L during treatment adjustment.
- 2) Proportion of isCGM stored glucose data < 2.8mmol/L during treatment adjustment.
- 3) Proportion of isCGM stored glucose data > 10.0mmol/L during treatment adjustment.
- 4) Proportion of glucose stored in isCGM > 13.3mmol/L during treatment adjustment.
- 5) The area of glucose in AGP map under the curve of < 10.0mmol/L during treatment adjustment.
- 6) The area of glucose in AGP map under the curve of < 3.9 mmol/L during treatment adjustment.
- 7) Mean value of isCGM stored glucose data during treatment adjustment (MEAN).
- 8) Standard deviation (SD) of isCGM stored glucose data during treatment adjustment.
- 9) Differences between physician approved dose and algorithm recommended dose in intervention group.
- 10) Number of physician overrides in the intervention group.
- 11) In the intervention group, if physician overrides occurred, the proportion of glucose within the range of 3.9mmol/L to 10.0mmol/L within 4 hours after insulin injection.
- 12) In the intervention group, if physician overrides occurred, the sensor glucose level at 4 hours after insulin injection.

4 General considerations

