5.4 Graphical analysis

To clearly present the between-arm differences of the endpoints, a forest plot will also be provided for the isCGM derived endpoints. Besides, a comparison plot of isCGM glucose pattern between the two arms during the study period will also be presented, where the hypoglycemia events (< 3.0 mmol/L (54 mg/dL)), median, areas enclosed by 25%-75% and 5%-90% quantiles of sensor glucose level of each arm will be plotted. Finally, to compare the insulin dosage recommended by AP-A with the actual executed dosage, a Bland-Altman plot of the agreement between proposed and actual administered insulin dosage will be provided, together with a plot of the differences between proposed and actual administered insulin dosage during the titration period for each participant, where the differences between proposed and actual administered insulin dosage will be represented as dots, and the sizes of the dots will be proportional to their frequency. Besides, the median line (smoothed) of differences during the titration period will also be provided. Finally, the zone enclosed by the

10% and 90% quartile lines (smoothed) of the differences during the titration period will also be presented, and the number of the differences in each titration day will be identified in the plot. The pseudo-codes for the aforementioned plots are provided as follows:

Algorithm 1 Pseudo-code of the forest plot using R

Require: Data of the isCGM derived endpoints for each arm, data of the between-arm differences (mean (95% CIs)) of the isCGM derived endpoints

Ensure: A forest plot for the isCGM derived endpoints

- 1: Read data as $fp \leftarrow \text{read.csv}(\text{"data address"})$ in R
 - 2: Determine the style of forest plot $Data \leftarrow \text{fpShapesGp}(\text{lines}, \text{box})$ in R
 - 3: Output forest plot $\leftarrow \text{forestplot}(fp, \text{options}, \text{style})$ in R
 - 4: return
-

Algorithm 2 Pseudo-code of the comparison plot of isCGM glucose pattern between the two arms using Matlab

Require: isCGM data files for the two arms

Ensure: Comparison plot of isCGM glucose pattern between the two arms

- 1: for each file in the AP-A arm do
 - 2: Get isCGM data
 - 3: Get isCGM data sampling time
 - 4: for $i = 1$ to the length of isCGM data
 - 5: if i th isCGM data < 54 mg/dL
 - 6: $n_a \leftarrow n_a \cup i$ th isCGM data sampling time
 - 7: end
 - 8: Determine the location of i th isCGM data in the day (24h) according to its sampling time

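### Safety is tested only as sensor exposure; no clinical event is compared by arm, so short treated lows add little to the endpoint and treated or severe events go unreported

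*Supplement*

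**What the plan says.** The final SAP, section 1, sets out to determine whether algorithm-guided adjustment under physician supervision "is as effective and safe as those guided by physicians alone".

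Section 3.1 names one safety measure: "The primary safety endpoint is the percentage time spent with sensor glucose level below 3.0 mmol/L (54 mg/dL"). Section 5.2 gives its rule: "non-inferiority will be established if the upper bound of the CI does not greater than the non-inferiority margin of 2" percent. The interval is for a difference of medians: "between-group differences of the median will be calculated by bootstrap method (1000 replications").

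The other planned measures are these:

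- Secondary endpoints 1 to 8 (section 3.2) are proportions, areas, a mean and an SD of stored sensor glucose. The one for marked hyperglycaemia is typical: "Proportion of glucose stored in isCGM > 13.3mmol/L during treatment adjustment".
- Endpoints 9 and 10 describe dose differences and overrides in the algorithm arm only.
- Endpoints 11 and 12 are sensor glucose in the 4 hours after an injection.
- Section 5.4 uses the word events, but for sensor readings in a plot: "where the hypoglycemia events (< 3.0 mmol/L (54 mg/dL)), median, areas enclosed by" quantile bands.

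The protocol's outcome list and data analysis section add no clinical event.

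**The concern.** The trial evaluates an insulin-dosing tool in inpatients and intends to speak to its safety. Time below 3.0 mmol/L depends both on how often dosing leads to a low and on how long each low lasts. If a low is treated when seen, its duration is cut and it adds little to the endpoint, although it did occur and needed a response.

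No planned comparison would show that one arm had more lows that were treated or needed another person's help, more hyperglycaemic crises or more serious adverse events. A report that followed the plan could conclude that the algorithm is as safe as the physicians without giving any of these counts.

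**Working it through.** **The plan's own figure.** The only derived figure is the sample size of 106, for the efficacy endpoint, with a 7.5-point margin, 90% power, no true difference and "a one-sided significance level of 5% and SD of 13" percent. The SAP formula gives n = 2 × (1.645 + 1.282)² × 13² / 7.5² = 51.5, so 52 per arm (104). The noncentral-t version gives 53 per arm, 106 in total, with power 90.4%. The figure reproduces and is not affected by this point. The documents give no calculation for the safety endpoint.

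**Inputs for the safety endpoint**

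- Observation time: 7 days. The protocol's Study Procedures say "We assume that the hospitalization period is 7 days, and the titration period will be 7 days". This is 7 × 24 × 60 = 10,080 minutes.
- Margin: 2 percentage points (SAP 5.2).
- Reading interval: 15 minutes, an assumption. The algorithm's model uses this sampling period, but the sensor's storage interval is not stated.
- Length and number of lows: assumptions throughout; the documents give none.

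**Step 1: the margin in minutes.** 0.02 × 10,080 = 201.6 minutes per participant, or 28.8 minutes a day.

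**Step 2: what one low contributes.** Points added = 100 × duration / 10,080. Lows needed to reach the margin = 201.6 / duration.

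| Duration of low | Points added | Lows per participant to reach 2 points |
|---|---|---|
| 15 min | 0.149 | 13.4 |
| 30 min | 0.298 | 6.7 |
| 60 min | 0.595 | 3.4 |

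An excess of 13 one-reading lows per participant is 13 × 0.149 = 1.93 points, still below the margin. This concerns the size of the difference. The rule uses the upper confidence limit, so somewhat fewer lows would already put the result in doubt.

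**Step 3: the SAP rule under assumed rates.** Trials were simulated with 59 and 60 participants per arm, 400 trials per scenario and 1000 bootstrap replications each. Each low lasted 15 or 30 minutes. In the control arm 10% had any low, averaging 2 each.

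| Algorithm arm | Runs passing the safety test | Mean upper limit (points) |
|---|---|---|
| 40% with any low, about 2 each | 100% | 0.12 |
| 80% with any low, about 3 each | 100% | 0.65 |
| All with lows, about 5 each | 100% | 1.22 |

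A 95% interval for the difference in means also passed in 100% of runs in all three scenarios. For short lows the insensitivity therefore comes from measuring time, not from using medians.

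**Step 4: does another planned output count events?** For each arm, the pseudo-code for the glucose-pattern plot (Algorithm 2) stores the time of every reading below 54 mg/dL and plots it. It does not join readings into episodes, count them per participant or compare the counts. No section tabulates a clinical event.

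**Step 5: what an event table could show.** The documents do not give the split of the 119 enrolled; 59 and 60 is assumed from the 1:1 allocation. With 0 events in 59, the upper limit of the exact two-sided 95% interval is 1 − 0.025^(1/59) = 6.1%. At 59 per arm and two-sided 5%, power is about 18% for 5% against 10%, and 44% for 5% against 15%. Reaching 80% power would take about 435 and 141 per arm. The table can describe but cannot test.

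**The case against.** The strongest reply is that safety is tested. Time below 3.0 mmol/L is a co-primary endpoint with a margin. Proportions below 3.9 and 2.8 mmol/L and above 10.0 and 13.3 mmol/L are compared by arm, and readings below 3.0 mmol/L are plotted for each arm. This stands. A reader might infer that the plan leaves safety untested; sections 3.1 and 5.2 contradict that.

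A reader might also infer that unmasked staff ended lows sooner in the arm they watched more closely. Nothing in the documents shows this. Both arms wear the sensor, and physicians decide or approve doses in both. No passage describes how lows are handled on the ward.

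Third, a large hidden excess is hypothetical. One extra one-reading low per participant per day would make 7 × 60 = 420 events in an arm of 60, but it would also add 7 × 0.149 = 1.04 points, half the margin, and every such reading would appear in the plot. The documents give no basis for that rate.

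Fourth, charted treatment is itself open to bias. Unmasked staff decide on it and record it, whereas the sensor records automatically. This stands, and is why the fix adds a sensor episode count.

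Finally, title, consent and other pages were removed, and adverse-event collection may be described there. Only the absence of a planned by-arm analysis in the visible sections is supported, not a claim that events were never collected.

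**Conclusion.** The point holds in a limited form. The final SAP tests safety only as sensor exposure, and no clinical event is compared by arm in the visible outcome and analysis sections of either document. Short lows ended by treatment add about 0.15 points each, if readings are 15 minutes apart and observation lasts 7 days. Treated or severe events have no planned report.

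The table and simulations show what the endpoint could fail to reveal under assumed rates and durations; they do not show that an excess occurred. The efficacy analysis and the sample size of 106 are untouched. Whether the 2-point margin and the difference of medians suit this endpoint is a separate question that an event table does not settle.

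**What to change.** Add to SAP 3.2 and 5.3 a descriptive table by arm for the in-hospital titration period, taken from ward charts. Give participants and events, with exact 95% confidence intervals for the proportions of participants affected, for:

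- hypoglycaemia needing another person's help;
- hypoglycaemia for which treatment was given, with a note that unmasked staff decide and chart it;
- hyperglycaemic crisis;
- serious adverse events.

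Beside it, give the number of distinct sensor episodes below 3.0 mmol/L per participant, with the rule for joining consecutive readings stated. This count does not depend on charting.

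Show events from discharge to day 14 separately, with the number of participants followed. After discharge both arms follow physician instructions, so pooling those days would dilute a difference. Follow-up may also be incomplete: the summary of SAP changes says glycated albumin, planned for the day-14 visit, was not obtained from more than half of participants.

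Word the conclusion as non-inferiority in sensor time below 3.0 mmol/L, with clinical events reported alongside. Do not make the table a pass/fail gate: it has no margin, little power, and would be added after enrolment.

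The cost is chart extraction for 119 short admissions, one table and one derived sensor variable, with no new procedure for participants. Intervals will be wide: 0 of 59 still allows up to about 6%.
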